3.4 Primary Safety Endpoints

- Type, frequency, severity and relationship of the adverse events to apremilast
- Number of subjects who prematurely discontinue treatment due to any adverse event
- Frequency of clinically significant changes in vital signs and/or laboratory findings

4 Subject Selection Enrollment and Withdrawal

4.1 Inclusion Criteria

1. Male and female subjects between 18 and 70 years of age
2. Oral ulcers that occurred at least monthly in the 6 month period prior to enrollment
3. Had at least 2 oral ulcers in the 4 weeks prior to enrollment at baseline
4. At least 3 oral ulcers during an ulcer flare
5. Patients must be candidates for systemic therapy for the treatment of oral ulcers, those that are considered unsuitable for topical therapy alone based on severity of disease, or whose oral ulcers cannot be adequately controlled with topical therapy.
6. Female premenopausal subjects must use one of the approved contraceptive options while taking apremilast and for at least 28 days after administration of the last dose of apremilast
7. Patients are able and willing to provide written informed consent after the nature of the study is fully explained.
8. No evidence of systemic disease

4.1.1 Contraception Requirements

Females of childbearing potential^a (FCBP) must have a negative pregnancy test at screening. While on investigational product and for at least 28 days after taking the last dose of investigational product, FCBP who engage in activity in which conception is possible must use one of the approved contraceptive options described below:

Option 1 - Any one of the following highly effective methods: hormonal contraception (oral, injection, implant, transdermal patch, vaginal ring); intrauterine device (IUD); tubal ligation; or partner's vasectomy;

OR

Option 2 - Male or female condom (latex condom or nonlatex condom NOT made out of natural [animal] membrane [for example, polyurethane]; PLUS one additional barrier method: (a) diaphragm with spermicide; (b) cervical cap with spermicide; or (c) contraceptive sponge with spermicide.

^a A female of childbearing potential is a sexually mature female who has not undergone a hysterectomy or bilateral oophorectomy or has not been postmenopausal for at least 24 consecutive months.

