HIPAA	Health Insurance Portability and Accountability Act
IB	Investigator's Brochure
IRB	Institutional Review Board
PHI	Protected Health Information
PI	Principal Investigator
RAS	Recurrent Aphthous Stomatitis
SAE	Serious Adverse Event/Serious Adverse Experience
SOP	Standard Operating Procedure

Study Summary

Title	A Pilot Study Evaluating the Efficacy of Apremilast in the Treatment of Subjects with Severe Recurrent Aphthous Stomatitis (RAS)
Running Title	A Pilot Study on the use of apremilast for Recurrent Aphthous Stomatitis (RAS)
Protocol Number	N/A
Phase	Pilot
Methodology	
Overall Study Duration	24 weeks
Subject Participation Duration	24 weeks
Single or Multi-Site	Single Site
Objectives	Determination of treatment efficacy and safety of Apremilast in patients with RAS
Number of Subjects	15
Diagnosis and Main Inclusion Criteria	Males and females, between 18 and 70 years old, with Recurrent Aphthous Stomatitis (RAS)
Study Product, Dose, Route, Regimen	Apremilast 30mg orally twice daily for 16 weeks
Treatment duration	Sixteen weeks on active study. Posttreatment follow-up period of 8 weeks.
Statistical Methodology	Wilcoxon signed rank test for comparison of outcomes between treatments and McNemar's exact test for categorical outcome variables

1 Introduction

This document is a protocol for a human research study. This study will be carried out in accordance with the applicable federal regulations and Mayo Clinic research policies and procedures.

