3.1 General Design

The study will be a pilot study using apremilast 30mg orally twice daily, for treatment of RAS in males and females between 18 and 70 years old.

Subjects will be recruited from the clinical practice of the Department of Dermatology or Division of Rheumatology at Mayo Clinic Florida. Fifteen males and females with RAS will be enrolled.

The study will consist of 3 phases: a screening phase, a 16 week treatment phase and an 8 week posttreatment observational follow-up phase.

The screening phase will consist of: obtaining informed consent, demographic information, medical history, inclusion and exclusion criteria, prior and concomitant medication use, adverse events; collecting vital signs and weight; performing complete physical examination and limited physical examination; obtaining hematology, serum chemistry, urinalysis, pregnancy test and providing contraception education.

During the 16-week treatment phase, all subjects receive apremilast.

All subjects who complete the active treatment phase are to enter the 8-week posttreatment observational follow-up phase.

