3.1.1 Contraception Education

The risks to a fetus or to a nursing child from apremilast are not known at this time. Results of the animal and in vitro studies can be found in the IB.

All females of childbearing potential (FCBP) must use one of the approved contraceptive options as described in section 4.1.1 while on investigational product (IP) and for at least 28 days after administration of the last dose of the IP.

When a female subject of childbearing potential's contraceptive measures or ability to become pregnant changes at the time of study entry or at any time during the study, the Investigator will educate the subject regarding options and correct and consistent use of effective contraceptive methods in order to successfully prevent pregnancy.

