4.2 Exclusion Criteria

6/21/2017

1. Prior use of apremilast.
2. Use of any investigational drug within 4 weeks prior to randomization, or 5 pharmacokinetic/pharmacodynamic half-lives, if known (whichever is longer).
3. Having received concomitant immune modulating therapy 12 weeks prior to enrollment, systemic steroids 6 weeks prior to enrollment or topical steroids within 4 weeks prior to enrollment.
4. Pregnant women or breast-feeding mothers.
5. Systemic or opportunistic fungal infection.
6. Known active current or history of recurrent bacterial, viral, fungal, mycobacterial or other infections (tuberculosis and atypical mycobacterial disease, hepatitis B and C and herpes zoster, histoplasmosis, coccidiomycosis) or any major episode of infection requiring hospitalization or treatment with IV or oral antibiotics within 4 weeks of the screening phase.
7. History of positive test for, or any clinical suspicion of, human immunodeficiency virus (HIV), or congenital or acquired immunodeficiency.
8. History of depression.
9. Malignancy or history of malignancy, except for:
 - a - treated (ie, cured) basal cell or squamous cell in situ skin carcinomas;
 - b - treated (ie, cured) cervical intraepithelial neoplasia (CIN) or carcinoma in situ of cervix with no evidence of recurrence within the previous 5 years.
10. Other than disease under study, any clinically significant (as determined by the Investigator) cardiac, endocrinologic, pulmonary, neurologic, psychiatric, hepatic, renal, hematologic, immunologic disease, or other major disease that is currently uncontrolled.
11. Any condition, including the presence of laboratory abnormalities, which would place the subject at unacceptable risk if he/she were to participate in the study.
12. Prior history of suicide attempt at any time in the subject's life time prior to screening or randomization, or major psychiatric illness requiring hospitalization within the last 3 years.
13. Active substance abuse or a history of substance abuse within 6 months prior to screening.
14. Presence of any of the following vitamin deficiencies - B1, B2, B6, B12, vitamin C, zinc, folate, iron.
15. Celiac disease.
16. Inflammatory Bowel Disease.
17. Genital aphthous ulcers.
18. Behçet's disease.
19. History of positive patch test for allergic contact stomatitis.
20. Positive anti-endomysial or anti-gliadin antibodies.
21. A diagnosis of uveitis (current or previous).
22. Erythema nodosum-like lesions (current or previous).

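### No pregnancy test is required at week 0 before the first dose, so an unrecognised pregnancy that began after screening can be exposed to apremilast

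*Combined protocol and SAP*

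**What the plan says.** **Testing.** Section 4.1.1 requires that females of childbearing potential "must have a negative pregnancy test at screening". Section 3.1 places the same test in the screening phase, which ends with "pregnancy test and providing contraception education". The Schedule of Events (6.1) marks the test at screening and, as an option left to the investigator, at week 16. The week 0 cell is empty.

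**Week 0.** Section 6 item b lists a medical history, a limited examination, a re-check of the inclusion and exclusion criteria, adverse events, vital signs, weight, contraception education and the efficacy measures. Drug is then dispensed.

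**Timing.** Section 3.1 states: "The study will consist of 3 phases: a screening phase, a 16 week treatment phase and an 8 week posttreatment observational follow-up phase". Treatment and follow-up have lengths; screening does not.

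**Contraception.** Inclusion 6 reads: "Female premenopausal subjects must use one of the approved contraceptive options while taking apremilast", and it continues for at least 28 days after the last dose. Sections 3.1.1 and 4.1.1 set the same period. If a woman's contraception or ability to conceive changes, section 3.1.1 adds that "the Investigator will educate the subject regarding options and correct and consistent use of effective contraceptive methods".

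**Pregnancy and fetal risk.** Exclusion 4 is "Pregnant women or breast-feeding mothers". Section 3.1.1 states: "The risks to a fetus or to a nursing child from apremilast are not known at this time".

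**The concern.** Exclusion 4 matters most at the first dose, but the only test that supports it is done earlier, at a time the protocol does not limit. A woman can test negative at screening, conceive before week 0, answer every week 0 question truthfully, and be given drug.

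What is at stake is fetal exposure to a drug whose fetal risk the protocol itself calls unknown. Section 7.3.1 does stop drug at once for a confirmed or suspected pregnancy. However, it covers pregnancies that occur on study drug or within 30 days of the last dose, so in this situation it acts only after exposure. No later compulsory test would pick up what week 0 missed. This is a question of participant safety and does not touch the endpoint or its analysis.

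**Working it through.** The plan states no figure to reproduce, so the check sets its sections side by side.

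**1. Count of pregnancy tests**

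| Visit | Test | Source |
|---|---|---|
| Screening | Compulsory | 3.1; 4.1.1; section 6 item a; 6.1 |
| Week 0 (first dispensing) | None | section 6 item b; 6.1 |
| Weeks 2, 4, 8, 12 | None | section 6 items c to f; 6.1 |
| Week 16 | Optional | section 6 item g; 6.1 |
| Week 24 | None | section 6 item h; 6.1 |

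Compulsory tests before the first dose: 1 + 0 = 1. The visit descriptions and the schedule agree, so the empty week 0 cell is not a fault of the table.

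**2. Interval from test to first dose**

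- The Study Summary gives 24 weeks of participation and, for treatment duration, "Sixteen weeks on active study. Posttreatment follow-up period of 8 weeks".
- Time left for screening within participation: 24 − (16 + 8) = 0 weeks.
- Zero weeks may hint that a short screening phase was intended. It does not cap the interval, because screening is simply not counted.
- A zero interval is unlikely. This is an inference: screening and week 0 are separate visits, and exclusion 14 (vitamin and mineral deficiencies) depends on results from blood taken at screening (section 6 item a).
- Nothing rules out a longer interval. Exclusion 3 has washouts of 4 to 12 weeks and section 5.4 has one of 3 months, all counted back from enrollment, and the protocol does not say whether a patient may be screened before or during a washout.

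**3. What protects the interval**

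| Safeguard | Effect between screening and first dose |
|---|---|
| Contraception rule (3.1.1, inclusion 6, 4.1.1) | Starts with drug; does not apply before it |
| Contraception education at screening and week 0 | Lowers the chance of conception; detects nothing |
| Medical history and eligibility re-check at week 0 | Finds a known pregnancy, not an unrecognised one |
| Immediate discontinuation (7.3.1) | Acts only once the woman is on drug |

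No row detects an unrecognised pregnancy before dosing.

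**4. Number exposed to the gap**

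The number of females of childbearing potential among the 15 subjects is not stated, so it lies between 0 and 15. The documents give neither the interval nor a conception rate, so no expected number of exposed pregnancies can be calculated.

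**The case against.** The strongest reply is that the interval is better protected than a literal reading suggests. Inclusion 6 is an eligibility criterion, and eligibility is checked at both screening and week 0, so a woman must have a method in place when drug is dispensed. Education is given at both visits. The 24-week total hints at a short screening phase, and with 15 subjects at one site the chance of an affected pregnancy may be very small. The Investigator's Brochure and the separate monitoring plan (9.1) are not available and could bear on the fetal risk or add checks. A week 0 test can also miss a very recent conception, and repeating it leaves 16 weeks of dosing without a compulsory test.

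Most of this stands as a limit on the size of the risk. It does not close the gap. Having a method in place at dispensing says nothing about the preceding days or weeks: Option 2 in 4.1.1, a condom plus a second barrier, can be started on the day of the first dose. A probably short interval is still an unlimited one. Nothing in the protocol shows that the unseen documents contain a week 0 test. The imperfect sensitivity of a repeat test means that the remedy reduces the risk without removing it. The lack of compulsory testing during treatment is a separate matter: contraception is at least mandatory then, as it is not before the first dose.

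**Conclusion.** The concern holds. The protocol requires one negative pregnancy test, at screening, none at week 0, and sets no maximum time between that test and the first dose. Followed exactly, it allows an unrecognised pregnancy to be exposed to apremilast despite exclusion 4.

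Confidence is high for the gap in the text and does not extend to the probability of harm. That probability depends on the screening interval and on the number of females of childbearing potential (0 to 15), and neither is given. The conclusion assumes that no document outside the protocol supplies a week 0 test, and that some time passes between screening and week 0, as the dependence on screening blood results suggests. An investigator may choose to test at week 0, but nothing requires it. The change should be made because the possible consequence is serious and the remedy is small. No efficacy result is affected.

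**What to change.** Require a negative urine pregnancy test at week 0, before drug is dispensed, for every female of childbearing potential. The edits go in three places: section 4.1.1, section 6 item b, and the week 0 cell of the pregnancy test row in the Schedule of Events. A lighter alternative is to require the week 0 test only when the screening test is older than a stated few days, with that limit written into 4.1.1.

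The cost is one urine test per eligible woman at a visit that already takes place: 0 to 15 tests among the 15 enrolled, and fewer under the alternative. No new visit or invasive procedure is needed. The drawback is the extra test itself and a short wait for its result before dispensing.

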4.2 Exclusion Criteria

6/21/2017

1. Prior use of apremilast.
2. Use of any investigational drug within 4 weeks prior to randomization, or 5 pharmacokinetic/pharmacodynamic half-lives, if known (whichever is longer).
3. Having received concomitant immune modulating therapy 12 weeks prior to enrollment, systemic steroids 6 weeks prior to enrollment or topical steroids within 4 weeks prior to enrollment.
4. Pregnant women or breast-feeding mothers.
5. Systemic or opportunistic fungal infection.
6. Known active current or history of recurrent bacterial, viral, fungal, mycobacterial or other infections (tuberculosis and atypical mycobacterial disease, hepatitis B and C and herpes zoster, histoplasmosis, coccidiomycosis) or any major episode of infection requiring hospitalization or treatment with IV or oral antibiotics within 4 weeks of the screening phase.
7. History of positive test for, or any clinical suspicion of, human immunodeficiency virus (HIV), or congenital or acquired immunodeficiency.
8. History of depression.
9. Malignancy or history of malignancy, except for:
 - a - treated (ie, cured) basal cell or squamous cell in situ skin carcinomas;
 - b - treated (ie, cured) cervical intraepithelial neoplasia (CIN) or carcinoma in situ of cervix with no evidence of recurrence within the previous 5 years.
10. Other than disease under study, any clinically significant (as determined by the Investigator) cardiac, endocrinologic, pulmonary, neurologic, psychiatric, hepatic, renal, hematologic, immunologic disease, or other major disease that is currently uncontrolled.
11. Any condition, including the presence of laboratory abnormalities, which would place the subject at unacceptable risk if he/she were to participate in the study.
12. Prior history of suicide attempt at any time in the subject's life time prior to screening or randomization, or major psychiatric illness requiring hospitalization within the last 3 years.
13. Active substance abuse or a history of substance abuse within 6 months prior to screening.
14. Presence of any of the following vitamin deficiencies - B1, B2, B6, B12, vitamin C, zinc, folate, iron.
15. Celiac disease.
16. Inflammatory Bowel Disease.
17. Genital aphthous ulcers.
18. Behçet's disease.
19. History of positive patch test for allergic contact stomatitis.
20. Positive anti-endomysial or anti-gliadin antibodies.
21. A diagnosis of uveitis (current or previous).
22. Erythema nodosum-like lesions (current or previous).
23. An established diagnosis of a systemic disease (SLE, Reiter's, Sweet's and MAGIC syndrome).

4.3 Subject Recruitment, Enrollment and Screening

Subjects will be recruited from the clinical practice of the Department of Dermatology or Division of Rheumatology, Mayo Clinic Florida. Patients seeking treatment for RAS will be offered standard conservative medical therapy for RAS as part of routine dermatological treatment. As an alternative, patients will be informed of the study protocol, and offered the option to enroll if they meet the study eligibility criteria.

4.4 Early Withdrawal of Subjects

4.4.1 When and How to Withdraw Subjects

Subjects may withdraw from the study at any time for the following:

- Subject safety issues related to serious reactions such as bacterial or viral skin infection, fever, or tissue hypertrophy.
- Subject decision to withdraw from the study (withdrawal of consent)
- Subject's decision to pursue other therapeutic regimens, either surgical or non-surgical

4.4.2 Data Collection and Follow-up for Withdrawn Subjects

Even though a subject has withdrawn from the study, it will be important to collect follow-up or survival data on subjects throughout the protocol defined follow-up period. Such data are important to the integrity of the final study analysis. If a subject withdraws consent to participate in the study for subject safety reasons, attempts will be made to obtain permission to collect follow up information whenever possible. Patients will be analyzed by intention to treat principles.

5 Study Drug

5.1 Description

Apremilast is an oral small-molecule inhibitor of phosphodiesterase (PDE) 4 that works intracellularly to modulate a network of pro-inflammatory and anti-inflammatory mediators. PDE 4 is a cyclic adenosine monophosphate (cAMP)-specific PDE and the dominant PDE in inflammatory cells. PDE4 inhibition elevates intracellular cAMP levels, which in turn down-regulates the inflammatory response by modulating the expression of TNF- α , IL-23, IL-17 and other inflammatory cytokines. Cyclic AMP also modulates levels of anti-inflammatory cytokines such as IL-10. Apremilast has immunomodulatory activity and, therefore, has the potential to be effective in the treatment of RAS.

5.2 Treatment Regimen

Subjects will receive apremilast 30mg twice daily for 15 weeks. Since Apremilast is known to be associated with gastrointestinal side effects and headaches, the dose will be increased gradually in the first week according to the following schedule:

Day 1: 10mg in morning

Day 2: 10mg in morning and 10mg in evening

Day 3: 10mg in morning and 20mg in evening

Day 4: 20mg in morning and 20mg in evening

Day 5: 20mg in morning and 30mg in evening

Day 6 and thereafter: 30mg twice daily

5.3 Administration of Study Drug

Subjects will receive apremilast 30mg twice daily orally for 15 weeks after 1 week of titration. Patients will be advised to take the medication in the morning and evening, with water.

5.4 Prior and Concomitant Therapy

Subjects will be allowed the following concomitant therapies to control flares: Tylenol, lidocaine 2% topical mouth wash and lidocaine 2% plus diphenhydramine plus Maalox topical mouth wash.

No topical and systemic therapies for RAS may be used 3 months prior to study enrollment.

6 Study Procedures

- a. The screening phase will consist of: obtaining informed consent, demographic information, medical history, inclusion and exclusion criteria, prior and concomitant medication use, adverse events; collecting vital signs and weight; performing complete physical examination, hematology, serum chemistry (vitamins B1, B6, B12, C, iron, folate, zinc, TTG, ANA), urinalysis, pregnancy testing, contraception education. Patients will also be assessed in regards to number of oral ulcers and pain visual analog scale for oral ulcers. A diary will be provided to the patient for keeping record of number and pain intensity of oral ulcers throughout the study.
- b. At baseline (week 0) all patients will undergo a complete medical history and limited physical examination, suitability assessment (inclusion and exclusion criteria), and safety assessments (adverse events, vital signs, weight, contraception education). Patients will also be assessed in relation to number of oral ulcers, pain visual analog scale for oral ulcers, physician's global assessment of oral lesions and Chronic Oral Mucosal Disease Questionnaire – COMDQ) and the investigational product will be dispensed.
- c. At week 2 all patients will undergo safety assessments (adverse events, vital signs, weight, and contraception education), efficacy assessments (number of oral ulcers, pain visual analog scale for oral ulcers, physician's global assessment of oral lesions) and investigational product accountability.
- d. At week 4 all patients will undergo safety assessments (adverse events, vital signs, weight, and contraception education), efficacy assessments (number of oral ulcers, pain visual analog scale for oral ulcers, physician's global assessment of oral lesions) and investigational product accountability. The investigational product will be dispensed.
- e. At week 8 all patients will undergo safety assessments (adverse events, vital signs, limited physical examination, weight, contraception education, and optional lab work per Investigator's discretion, including hematology and serum chemistry), efficacy assessments (number of oral ulcers, pain visual analog scale for oral ulcers, physician's global assessment of oral lesions and Chronic Oral Mucosal Disease Questionnaire – COMDQ) and investigational product accountability. The investigational product will be dispensed.
- f. At week 12 all patients will undergo safety assessments (adverse events, vital signs, weight, and contraception education) and efficacy assessments (number of oral ulcers, pain visual analog scale for oral ulcers and physician's global assessment of oral lesions) and investigational product accountability. The investigational product will be dispensed.
- g. At week 16 all patients will undergo safety assessments (adverse events, vital signs, weight, complete physical examination, contraception education and optional lab work per Investigator's discretion, including pregnancy testing, hematology and serum chemistry), efficacy assessments (number of oral ulcers, pain visual analog scale for oral ulcers, physician's global assessment of oral lesions and Chronic Oral Mucosal Disease Questionnaire – COMDQ) and investigational product accountability.
- h. At week 24 patients will undergo safety assessments (vital signs, weight, and complete physical examination) and efficacy assessments (number of oral ulcers, pain visual analog scale for oral ulcers, physician's global assessment for oral lesions and Chronic Oral Mucosal Disease Questionnaire - COMDK).

6/21/2017

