1.4 Dose Rationale and Risk/Benefits

Based on the safety and efficacy of previous studies using apremilast for Behçet's disease and psoriasis, the dose of apremilast 30mg was chosen for the present study. Subjects will receive apremilast 30mg twice daily for 16 weeks. Since apremilast is known to be associated with gastrointestinal side effects and headaches, the dose will be increased gradually during the first week of treatment until the full 30mg dose is reached.

The expected benefits from apremilast use include reduction in the number and duration of oral ulcers, decreased oral ulcer pain, improved physical function and quality of life in patients with RAS. Risks associated with apremilast therapy include possible gastrointestinal side effects, headaches, upper respiratory tract infection, hypersensitivity reactions and depression.

2 Study Objectives

Primary Objective

- To evaluate the efficacy of apremilast for the treatment of RAS.

Secondary Objectives

- To evaluate the safety and tolerability of apremilast in subjects with RAS.

3 Study Design

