6.1 Apremilast table of events**Schedule of Events**

Procedure	Screening phase	Baseline (Week 0)	Week 2	Week 4	Week 8	Week 12	Week 16	Week 24
Informed Consent	X							
Demography	X							
Medical History	X	X						
Inclusion/Exclusion Criteria	X	X						
Safety Assessments								
Adverse Events	X	X	X	X	X	X	X	
Vital Signs	X	X	X	X	X	X	X	X
Complete Physical Examination	X						X	X
Limited Physical Examination	X	X			X			
Weight	X	X	X	X	X	X	X	X
Hematology	X				X*		X*	
Serum Chemistry	X				X*		X*	
Urinalysis	X							
Pregnancy test	X						X*	
Contraception Education	X	X	X	X	X	X	X	
Efficacy Assessments								
Number of Oral Ulcers	X	X	X	X	X	X	X	X
Pain VAS for oral ulcers	X	X	X	X	X	X	X	X
Physician's Global Assessment of Oral Lesions	X	X	X	X	X	X	X	X
Chronic Oral Mucosal Disease Questionnaire – COMDQ	X	X			X		X	X
Investigational Product								
Dispense IP		X		X	X	X		
IP Accountability	X		X	X	X	X	X	

* lab work, including pregnancy testing, is optional per Investigator's discretion.

Statistical Plan

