6.3 Statistical Methods

Data Analysis – Given the design, all statistical analysis will be descriptive. Continuous outcome measures will be summarized using the sample mean, standard deviation, median, minimum, 25th and 75th percentiles, and maximum. Categorical variables will be summarized with number and percentage. 95% confidence intervals (CIs) will be estimated where appropriate.

Descriptive Statistics

We will summarize continuous variables using the sample mean, standard deviation, median, minimum, 25th and 75th percentiles, and maximum. We will summarize categorical variables with number and percentages. Ordinal variables will be summarized using the sample median, minimum, 25th and 75th percentiles, and maximum, as well as with number and percentage.

Handling of Missing Data

Given the prospective nature of the study, we expect to encounter little if any missing data. However in the event of missing data, no attempt to impute this missing data will be made in this pilot study; missing data will be treated as missing.

Multiplicity

No adjustment for multiple testing will be made owing to the exploratory, pilot nature of the study.

Primary Hypothesis:

We hypothesize that apremilast administration for RAS will decrease the number of ulcers at the end of treatment compared to baseline.

The primary endpoints of the study is the change in number of ulcers at the end of treatment compared to baseline.

The secondary endpoints of the study, occurrence of adverse reactions and morbidity, are both dichotomous categorical variables. As such, the proportion for which these outcomes occur will be estimated along with 95% confidence interval.

Interim Analysis

No interim analysis will be performed in this pilot study.

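### Week 24 omits the adverse event assessment that 7.1 and 7.2 require; as a minor point, 3.4 should say that laboratory changes describe only the subjects tested

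*Combined protocol and SAP*

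**What the plan says.** **Adverse events.** Section 3.4 lists among the safety endpoints "Type, frequency, severity and relationship of the adverse events to apremilast". Section 3.1 states "All subjects who complete the active treatment phase are to enter the 8-week posttreatment observational follow-up phase", and the only visit scheduled in that phase is week 24. For that visit section 6, item h, states "At week 24 patients will undergo safety assessments (vital signs, weight, and complete physical examination". Adverse events are not in the list, although items a to g each include them. The 6.1 table agrees with the text: its Adverse Events row is marked from screening to week 16 and blank at week 24.

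Section 7.1 ends the monitoring period at the end of follow-up and requires new, clinically significant end-of-study findings to be recorded as adverse events when they meet the definition. Section 7.2 obliges the team to ask specifically about adverse events whenever it is in contact with a subject, and to record every event in the study period.

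**Laboratory findings.** Section 3.4 also names "Frequency of clinically significant changes in vital signs and/or laboratory findings". Hematology and serum chemistry are required at screening. At week 8 (item e) and week 16 (item g) they are left to the investigator; item g reads "discretion, including pregnancy testing, hematology and serum chemistry", and the footnote to 6.1 says "lab work, including pregnancy testing, is optional". Urinalysis is marked at screening only. Section 6.3 adds that "missing data will be treated as missing".

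**The concern.** The schedule is what visit forms and coordinators usually follow. If week 24 is run from item h and the table, nobody is prompted to ask about events since week 16. The complete physical examination at that visit is only a partial substitute. Section 1.4 names the risks as "possible gastrointestinal side effects, headaches, upper respiratory tract infection, hypersensitivity reactions and depression", and several of these (gastrointestinal effects, headaches, depression) are learned mainly by asking. The diary in item a covers ulcer number and pain, so it does not fill the gap either.

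The statistical consequence has a direction. An event that nobody asks about does not appear as a missing value; the subject is simply counted as having had no event. The missing-data rule in 6.3 therefore gives no protection, and the adverse event frequency in 3.4 can only be understated.

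For laboratory changes the issue is the denominator. Tests ordered at discretion, with no stated criterion, may be ordered mainly where there is clinical concern. A frequency given without the number tested would be hard to interpret.

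**Working it through.** The plan states no figure to reproduce here. The check is a row-by-row comparison of section 6 and the 6.1 table with 3.4, 7.1 and 7.2.

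**1. Counts from the 6.1 table** (8 columns: screening, baseline, weeks 2, 4, 8, 12, 16, 24)

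| Row | Visits marked | Week 24 |
|---|---|---|
| Adverse Events | 7 of 8 | blank |
| Vital Signs | 8 of 8 | marked |
| Weight | 8 of 8 | marked |
| Complete Physical Examination | 3 of 8 (screening, weeks 16 and 24) | marked |
| Hematology, Serum Chemistry | 1 required (screening), 2 optional (weeks 8 and 16) | blank |
| Urinalysis | 1 of 8 (screening) | blank |

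The text of item h matches the blank Adverse Events cell, so the blank is not an artefact of reading the table from PDF.

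**2. Time without a scheduled assessment.** Treatment lasts 16 weeks and follow-up 8 (3.1): 16 + 8 = 24. The last marked adverse event assessment is week 16. The gap is 24 − 16 = 8 weeks, and 8/24 = 33% of the 24 weeks. That window holds one scheduled contact, with adverse events listed at 0 of 1.

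**3. Is week 24 inside the monitoring period?** Section 7.1 sets follow-up at 6 months after enrollment: 365.25/2/7 = 26.1 weeks. Counted from baseline, week 24 is inside it. If enrollment were dated from screening, whose length is not given, the 6-month point would come before week 24 only if screening lasted more than 26.1 − 24 = 2.1 weeks. Even then, 7.1 ties the end of monitoring to the end of follow-up, and the each-contact rule in 7.2 does not depend on the date.

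**4. Effect on the analysis.** Section 6.3 plans a proportion with adverse reactions and a 95% confidence interval. Assuming all 15 subjects are treated, each subject wrongly counted as event-free lowers that proportion by 1/15 = 6.7 percentage points. This applies only to subjects whose first event falls in weeks 16 to 24 and goes unrecorded. Counts by type and severity under 3.4 lose every unrecorded event, first or not. The documents give no basis for estimating how many there would be.

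**5. Laboratory data.** Required values after screening: 0 tests at 0 of the 7 later visits, so no subject of the 15 is assured a post-treatment result. Vital signs are scheduled at all 8 visits, so that half of the 3.4 bullet is unaffected. The adverse event route does not supply the missing half: 7.1 makes a laboratory abnormality an adverse event only when it appeared as a severe reaction needing hospitalization or further intervention, and 7.2 concerns recording results that exist.

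**The case against.** **Week 24.** The best defence is that 7.2 is mandatory and week 24 is a contact, so the question must already be asked there. Section 7.1 also has the investigator, at the last scheduled visit, tell subjects to report later events, and it requires unresolved events to be followed, so some adverse event activity is clearly intended at week 24. This stands in part. A reader might infer from the blank cell that no adverse events are collected after week 16; the documents do not support that. What remains is a contradiction. Items a to g all list adverse events despite 7.2, so leaving them out at one visit can be read as deliberate. The last-visit instruction looks forward and does not replace asking about the preceding 8 weeks.

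**Laboratory part.** Discretionary testing is an open choice in a 15-subject descriptive pilot. The bullet in 3.4 joins vital signs and laboratory findings with and/or, so it can be reported as written. This also stands. A reader might infer that 3.4 promises a laboratory frequency for all treated subjects, or that the endpoint cannot be reported; neither follows from the text. Nor is it exact to call all later testing optional, since urinalysis is not scheduled again at all.

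A reader might also try to put numerical limits on the all-treated laboratory frequency. The documents do not say how many subjects will be tested. Testing every subject once would still not settle the frequency, because a single draw at week 8 or week 16 can miss a change at another time. Applying the missing-data rule in 6.3 to a test that was never ordered is itself an inference.

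The separate monitoring plan mentioned in 9.1 was not available and may add detail. It would not make the protocol's own sections agree.

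**Conclusion.** The week 24 point holds as an internal contradiction and should be corrected. The schedule omits adverse events at the only follow-up visit (7 of 8 visits listed, 8 of 24 weeks uncovered), while 7.1 and 7.2 require them. The harm is conditional: it arises only if the schedule is followed in preference to 7.2. In that case the 3.4 adverse event frequency is biased downward by an amount the documents do not let us estimate.

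The laboratory point is real but minor. No laboratory test after screening is required, so any laboratory frequency describes subjects tested at discretion, who may be a selected group. It needs a stated denominator, not a new endpoint. That these subjects are selected is plausible, but the plan neither states nor excludes it.

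**What to change.** 1. In section 6, item h, add adverse events to the week 24 safety assessments, and mark the week 24 cell of the Adverse Events row in 6.1. This brings the schedule into line with 7.1 and 7.2. Cost: one phrase and one table cell, with no added visit.

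2. Keep the vital signs frequency in 3.4. In 3.4 or 6.3, add a sentence saying that laboratory changes are reported among subjects with a post-screening value, that the number tested out of the number treated is shown at each visit, and that the result is not presented as a frequency for all treated subjects. Cost: one sentence and one extra count in the safety table, with no added blood draw.

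Whether laboratory testing after screening should become routine is for the sponsor to decide; the reporting change does not depend on it.
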